#### REVISION HISTORY

Date	Rev.	Author	Changes/Comments
2017 Aug 15	1.0	[REDACTED]	

Philips IGT Systems  Status: Final	Post-Market Clinical Study Plan  Contrast volume reduction during PCI with the use of Dynamic Coronary Roadmap	XCY607-130198 2017 Aug 15 Revision: 1.0 Page 2 of 16
---	---	---

Philips IGT Systems  Status: Final	Post-Market Clinical Study Plan  Contrast volume reduction during PCI with the use of Dynamic Coronary Roadmap	XCY607-130198 2017 Aug 15 Revision: 1.0 Page 4 of 16
---	---	---

## SUMMARY

Identification of study device
The Dynamic Coronary Roadmap is developed by Philips Medical Systems Nederland B.V., a Philips Healthcare company. The proposed Dynamic Coronary Roadmap is a new software package that assists the imaging of the coronaries during coronary interventions.
Study design
This is a prospective, non-randomized, unblinded, observational, single-center study.
A non-randomized study design has been chosen to get first insights in contrast reduction with the use of Dynamic Coronary Roadmap. This study will serve as a pilot study to power a pivotal study at a later stage.
The results of the study population will be compared with retrospective data generated before the Dynamic Coronary Roadmap was installed.
Objectives
Primary objective: To collect data on the amount of contrast used during PCI with the aid of Dynamic Coronary Roadmap to define a possible contrast reduction. The study will serve as a pilot for potential larger and/or multi-center follow-up studies to define a possible contrast reduction claim.
Secondary objective(s):

 
Assessing radiation usage during PCI with the aid of Dynamic Coronary Roadmap
 
Collecting patient demographics to further define the study population
 
Assessing procedure efficiency
 
Collecting procedural information to further define the study population
 

Primary and secondary endpoints
The primary endpoint in this study will be the amount of contrast volume used during the PCI procedure.
Secondary endpoints will be the radiation dosage, procedure efficiency, study population and procedural information. This information will help to define the study population and/or procedures better and will be used to design a pivotal trial at a later stage.
Main inclusion criteria

 
Subject undergoing a percutaneous coronary intervention
 
Subject 18 years of age or older, or of legal age to give informed consent per state or national law
 
•
 

Main exclusion criteria

 
Subject undergoing an emergency treatment
 
Primary angioplasty for acute ST segment elevation myocardial infarction.
 
Subject with contrast allergies
 
Subject with severe kidney disease (eGFR < 40 by Modification of Diet in Renal Disease (MDRD)/Cockcroft Gault clearance formula and/or upon decision by investigator)
 
Subject participates in a potentially confounding drug or device trial during the course of the study.
 
Prisoners, people who cannot legally give consent, pregnant women and breastfeeding women
 
•
 

No. of subjects
It is expected that 45 subjects (see section 5 Statistical considerations) are necessary to collect sufficient data for the evaluation of the objectives of this clinical study. The enrollment period is expected to last for 4 months. There are no criteria for the amount of subjects treated with Dynamic Coronary Roadmap R1.1 versus R2.0, since a differentiating effect on this study's endpoints is not expected.
Study procedures
Patients will receive standard medical treatment for their cardiac condition. During routine procedures, the physician may take angiograms for diagnosis which also serve as reference for device navigation. These angiograms will be automatically processed in the Dynamic Coronary Roadmap software and displayed as an overlay on the fluoroscopy for navigation support. In case a balloon catheter is used, the physician may

Philips IGT Systems Status: Final	Post-Market Clinical Study Plan Contrast volume reduction during PCI with the use of Dynamic Coronary Roadmap	XCY607-130198 2017 Aug 15 Revision: 1.0 Page 5 of 16
---	---	---

take cine images when deflating the balloon as part of the standard care. These images can automatically be enhanced with the software and displayed. There is no follow up required after the procedure.

Phase 1: This is the phase where the physicians and study personnel can get used to the device and its capabilities. This phase serves to gain experience with the device and define workflow changes for the second phase. The use of Dynamic Coronary Roadmap makes these workflow changes possible and necessary in order to reduce the amount of contrast volume. It is estimated that 20 patients are necessary to gain enough experience and assess the workflow improvements.

Phase 2: This phase will focus on the contrast volume reduction. The defined workflow changes from phase 1 will be implemented in order to reduce the use of contrast volume. The minimal amount of contrast and timing of dosing will be defined. All other doses need to be avoided, as long as clinically acceptable. It is estimated that 25 patients are necessary to gain enough data to support the primary endpoint. This dataset will be compared with retrospective data from 25 patients that were treated without Dynamic Coronary Roadmap, preferably in the same timeframe.

#### Follow up

Subjects are enrolled in the study for the duration of the interventional procedure. No follow-up is required per protocol. Patient will be followed according to regular clinical standard of care.

#### Duration of the study

The total duration of the study is expected to take approximately 4 months.

## 1. DEVICE DESCRIPTION

### 1.1. Summary description of the study device

The Dynamic Coronary Roadmap is developed by Philips Medical Systems Nederland B.V., a Philips Healthcare company. The proposed Dynamic Coronary Roadmap is a new software package that assists the imaging of the coronaries during coronary interventions.

Dynamic Coronary Roadmap Release 1.1 is a released software package (K170130) that can be used to support the navigation of interventional devices in the coronary arteries. Dynamic Coronary Roadmap allows the users to see a roadmap of the coronary anatomy displayed on live fluoroscopy. Dynamic Coronary Roadmap uses image registration techniques to provide an overlay of the coronary arteries (automatically derived from the coronary angiogram) on top of the live fluoroscopy (see Figure 1). It is intended to provide a Dynamic Coronary Roadmap for guidance and navigation of devices, providing additional confidence in the procedure, and possibly reducing the need for additional contrast puffs.

Dynamic Coronary Roadmap Release 2.0 introduces the FFR / iFR Roadmap feature. FFR/iFR Roadmap visualizes the position of the pressure wire and the coronary artery on an X-ray image at the moment that an intravascular blood pressure measurement was performed as well as the intravascular blood pressure measurement values themselves. Dynamic Coronary Roadmap Release 2.0 does not have 510(k) clearance yet.

Philips IGT Systems  Status: Final	Post-Market Clinical Study Plan  Contrast volume reduction during PCI with the use of Dynamic Coronary Roadmap	XCY607-130198 2017 Aug 15 Revision: 1.0 Page 6 of 16
---	---	---

Figure 1: On the left a standard fluoroscopy image and on the right a Dynamic Coronary Roadmap image with a coronary roadmap superimposed on a fluoroscopy image.

The study device includes the "Coronary tools" Dynamic Coronary Roadmap R1.1 and StentBoost Live R1.1 to permit full identification. Dynamic Coronary Roadmap R1.1 will be upgraded to R2.0 after FDA clearance of the FFR/iFR Roadmap feature.

[1] Note: StentBoost Live 1.1 is not used in the context of this post market study. Therefore it is not mentioned further in this post market study plan

The manufacturer of the study device is:

Philips Medical Systems Nederland B.V., a Philips Healthcare company  
[name]  
[name]  
The Netherlands

## 1.2. Intended Purpose

The sections below contain the information for Dynamic Coronary Roadmap. The only difference between the intended use of Dynamic Coronary Roadmap 1.1 and 2.0 is the FFR / iFR Roadmap feature. The changes due to the addition of the FFR / iFR Roadmap feature have been marked in *italic* font. Consequently,

- Normal text = Dynamic Coronary Roadmap 1.1; and
- Normal text + *italic* text = Dynamic Coronary Roadmap 2.0.

### 1.2.1. Product Description Dynamic Coronary Roadmap [1]

Dynamic Coronary Roadmap is a software medical device intended to provide a real-time and dynamic angiographic roadmap of coronary arteries.

The angiographic roadmap is automatically generated from previously acquired diagnostic coronary angiograms during the same procedure.

Dynamic Coronary Roadmap overlays the angiographic roadmap on live 2D fluoroscopic images, thereby assisting the physician in navigating devices, e.g. (guide) wires, catheters, through the coronary arteries.

*Dynamic Coronary Roadmap is to be used in combination with a Philips interventional X-ray system.*

*When also used in conjunction with a compatible intravascular blood pressure measurement system, Dynamic Coronary Roadmap offers an FFR/iFR Roadmap feature which combines the information of the blood pressure within a coronary artery with an X-ray image of the pressure wire within that coronary artery, acquired when the pressure measurement was performed.*

### 1.2.2. Indications for Use / Medical Purpose

Dynamic Coronary Roadmap is intended to assist the physician during percutaneous coronary interventions in correlating the device position to the coronary vasculature, by providing a motion compensated overlay of this coronary vasculature.

Philips IGT Systems  Status: Final	Post-Market Clinical Study Plan  Contrast volume reduction during PCI with the use of Dynamic Coronary Roadmap	XCY607-130198 2017 Aug 15 Revision: 1.0 Page 7 of 16
---	---	---

*The FFR/iFR Roadmap feature is intended to assist the physician during percutaneous coronary interventions in relating the intravascular blood pressure measurement to its anatomical location. FFR/iFR roadmap visualizes the position of the pressure wire and the coronary artery on an X-ray image at the moment that an intravascular blood pressure measurement was performed as well as the intravascular blood pressure measurement values themselves.*

Dynamic Coronary Roadmap is suitable for use with the entire adult human population.

#### 1.2.3. Intended Operator Profile

Dynamic Coronary Roadmap is intended to be used and operated by: adequately trained, qualified, and authorized healthcare professionals who have understanding of the safety information and emergency procedures as defined by local laws and regulations for radiation workers and staff.

#### 1.2.4. Clinical environment

Dynamic Coronary Roadmap is intended to be used in the cath lab, interventional suite or hybrid operating room. The software medical device is connected to a Philips interventional X-ray system. Additionally it may also be connected to a compatible intravascular blood pressure measurement system.

#### 1.2.5. General safety and effectiveness

To facilitate safe and effective operation of the system by a trained healthcare professional, instructions for use are provided as part of the device labeling.

Dynamic Coronary Roadmap is a software medical device and does not come in contact with a human subject.

The study device manual contains safety precautions and handling of the study device.

Note: the FFR / iFR Roadmap feature is disabled by means of a license in Dynamic Coronary Roadmap R1.1. The FFR / iFR Roadmap feature is enabled after upgrade to Dynamic Coronary Roadmap R2.0.

### 1.3. Necessary training and experience needed to use the research device

Dynamic Coronary Roadmap is intended to be used and operated by adequately trained, qualified, and authorized healthcare professionals who have understanding of the safety information and emergency procedures as defined by local laws and regulations for radiation workers and staff. Training on the study device is needed and will be provided by Philips upon delivery of the device. This training will be documented and filed in the Investigator Site File.

Note: as ON/ OFF of the study device is not automatically coupled to the ON/OFF of the Allura system, the user will be trained and will get a dedicated version of the IFU. There are no other differences between the study device and the "regular Coronary Tools".

### 1.4. Materials that will be in contact with tissues or body fluids

No materials of the study device will be in contact with tissue or body fluids.

### 1.5. Device Traceability

The study device includes Dynamic Coronary Roadmap R1.1 (will be upgraded to R2.0 after FDA approval) and Stentboost Live R1.1 to permit full identification. Device traceability will be maintained by Philips. Records shall be kept to document when the device is received, installed or returned/uninstalled/disposed at the hospital.

## 2. JUSTIFICATION FOR THE DESIGN OF THE STUDY

Dynamic Coronary Roadmap has been clinically evaluated in the Isala Klinieken, Zwolle, The Netherlands and in the Centre Cardiologique du Nord, St. Denis, France, respectively. The findings of the evaluations have been described in the following two reports:

Philips IGT Systems  Status: Final	Post-Market Clinical Study Plan  Contrast volume reduction during PCI with the use of Dynamic Coronary Roadmap	XCY607-130198 2017 Aug 15 Revision: 1.0 Page 8 of 16
---	---	---

Zwolle: "XCY607-130019 Clinical Study End Report.pdf" [5]

St. Denis: "XCY607-130044 Clinical Study End Report v1 Cardiac Roadmap.pdf" [6]

A Clinical Evaluation Report has been created for Dynamic Coronary roadmap R2 DHF287327 [7].

## 2.1. Clinical study Justification

The abovementioned evaluation in Zwolle took place prior to the evaluation in St. Denis. In short, the evaluation in Isala Klinieken, Zwolle, The Netherlands showed that in about 80% of the patients, a suitable roadmap could be generated for guidewire navigation. Philips made the decision to modify the software with the aim to improve the success rate. A new clinical evaluation was performed in Centre Cardiologique du Nord, St. Denis, France, where it was demonstrated that Dynamic Coronary Roadmap was capable of creating suitable roadmaps for guidewire navigation in 94% of the fluoroscopy usage for guidewire navigation. During this evaluation it became apparent an improved workflow is needed so that Dynamic Coronary Roadmap can be used in combination with StentBoost Live.

Dynamic Coronary Roadmap was pre-clinically tested in combination with StentBoost Live. The combination of these products was called PCI Express. The PCI Express software was aimed at workflow optimization. The workflow was tested pre-clinically using a set-up of PCI Express in combination with an X-ray system or X-ray simulator. A combination of phantoms and clinical images were used to mimic patients. Multiple users, including interventional cardiologists, clinical scientists and innovation scientists have evaluated the workflow of coronary angiography and intervention. The feedback was used to further optimize the workflow and design of the PCI Express.

The pre-clinical evaluations were a surrogate for testing PCI Express during coronary angiography or intervention. However, neither time critical procedure steps, the presence of and interaction between multiple people in the heart catheterization laboratory, nor the anatomy and physiology of patients could be emulated. Therefore, a final determination of the optimal workflow was done in a clinical setting. This new iteration of the device was evaluated in Universitäts Klinikum Düsseldorf [8]. The study aimed for evaluation of the usability and workflow of Dynamic Coronary Roadmap in combination with StentBoost Live. The improved workflow and usability were evaluated and no new risks were identified. Results showed that StentBoost Live can be used in combination with Dynamic Coronary Roadmap.

To our knowledge, there are no comparable devices for Dynamic Coronary Roadmap, capable to perform a dynamic superimposition of the coronary anatomy on live fluoroscopy.

## 3. OBJECTIVES AND HYPOTHESES

### 3.1. Primary objective

The primary objective of this clinical study is:

- To collect data on the amount of contrast used during PCI with the aid of Dynamic Coronary Roadmap to define a possible contrast reduction. The study will serve as a pilot for potential larger and/or multi-center follow-up studies to define a possible contrast reduction claim.

The objective is descriptive in nature and is intended to provide additional information. There will be no pass or fail criteria.

### 3.2. Secondary objective(s)

The secondary objective is/are:

- Assessing radiation usage during PCI with the aid of Dynamic Coronary Roadmap
- Collecting patient demographics to further define the study population
- Assessing procedure efficiency
- Collecting procedural information to further define the study population

The objectives are descriptive in nature and are intended to provide additional information. There will be no pass or fail criteria.

Philips IGT Systems Status: Final	Post-Market Clinical Study Plan Contrast volume reduction during PCI with the use of Dynamic Coronary Roadmap	XCY607-130198 2017 Aug 15 Revision: 1.0 Page 9 of 16
---	---	---

## 4. STUDY DESIGN

### 4.1. General

This is a prospective, non-randomized, unblinded, observational, single-center study.

A non-randomized study design has been chosen to get first insights in contrast reduction with the use of Dynamic Coronary Roadmap. This study will serve as a pilot study to power a pivotal study at a later stage.

The results of the study population will be compared with retrospective data generated before the Dynamic Coronary Roadmap was installed.

### 4.2. Study device exposure and comparators

The Dynamic Coronary Roadmap will not be in contact to the patient. The monitor of the system will be displayed to the physician during the procedure. The software is installed on a PC which is placed in the control room.

There are no additional devices or medications required for the study, other than the ones that are used as part of the standard of care.

### 4.3. Subjects

#### 4.3.1. In- and exclusion criteria

Subjects participating in the study will be carefully selected based on the next inclusion and exclusion criteria.

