##### 4.3.1.1. Inclusion criteria

- Subject undergoing a percutaneous coronary intervention
- Subject 18 years of age or older, or of legal age to give informed consent per state or national law

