##### 4.3.1.2. Exclusion criteria

- Subject undergoing an emergency treatment
- Primary angioplasty for acute ST segment elevation myocardial infarction.
- Subject with contrast allergies
- Subject with severe kidney disease (e-GFR < 40 by Modification of Diet in Renal Disease (MDRD)/Cockcroft Gault clearance formula and/or upon decision by investigator)
- Subject participates in a potentially confounding drug or device trial during the course of the study.
- Prisoners, people who cannot legally give consent, pregnant women and breastfeeding women

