#### 4.3.3. Enrollment

Subjects are considered to be enrolled in the study after they have signed the informed consent form. No study procedures will be performed before this moment.

Subjects are enrolled in the study for the duration of the interventional procedure. No follow-up is required per protocol. Patient will be followed according to regular clinical standard of care.

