### 4.4. Procedures

Patients will receive standard medical treatment for their cardiac condition. During routine procedures, the physician may take angiograms for diagnosis which also serve as reference for device navigation. These angiograms will be automatically processed in the Dynamic Coronary Roadmap software and displayed as an overlay on the fluoroscopy for navigation support. In case a balloon catheter is used, the physician may take cine images when deflating the balloon as part of the standard care. These images can automatically be enhanced with the software and displayed. There is no follow up required after the procedure.

Phase 1: This is the phase where the physicians and study personnel can get used to the device and its capabilities. This phase serves to gain experience with the device and define workflow changes for the second phase. The use of Dynamic Coronary Roadmap makes these workflow changes possible and necessary in order to reduce the amount of contrast volume. It is estimated that 20 patients are necessary to gain enough experience and assess the workflow improvements.

Phase 2: This phase will focus on the contrast volume reduction. The defined workflow changes from phase 1 will be implemented in order to reduce the use of contrast volume. The minimal amount of contrast and timing of dosing will be defined. All other doses need to be avoided, as long as clinically acceptable. It is estimated that 25 patients are necessary to gain enough data to support the primary endpoint. This dataset will be compared with retrospective data from 25 patients that were treated without Dynamic Coronary Roadmap, preferably in the same timeframe.

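### Phase 2 fixes who may enter but not who must be invited, so the 25 device patients may be an unrepresentative, possibly simpler, subset of eligible patients and bias the estimated contrast reduction

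*Protocol*

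**What the plan says.** Section 4.1 of the protocol describes the design: "This is a prospective, non-randomized, unblinded, observational, single-center study". It adds that the study is a pilot meant to power a later pivotal study.

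On entry, section 4.3.1 says: "Subjects participating in the study will be carefully selected based on the next inclusion and exclusion criteria". The clinical inclusion criterion in 4.3.1.1 is "Subject undergoing a percutaneous coronary intervention", with no limit on vessels, lesions or complexity. Section 4.3.1.2 removes emergency cases and primary angioplasty for STEMI, among others. Its severe kidney disease criterion carries the words "and/or upon decision by investigator".

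Section 4.3.3 fixes the moment of entry: "Subjects are considered to be enrolled in the study after they have signed the informed consent form". Section 4.3.4 gives the number of subjects. None of sections 4.3.1 to 4.3.4 says which eligible patients have to be approached, or that those not approached are recorded.

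Section 4.4 sets out Phase 2: "The defined workflow changes from phase 1 will be implemented in order to reduce the use of contrast volume", and then "All other doses need to be avoided, as long as clinically acceptable". On the comparator it says: "This dataset will be compared with retrospective data from 25 patients that were treated without Dynamic Coronary Roadmap, preferably in the same timeframe".

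Under section 5.1 the endpoint is contrast volume in ml, all Phase 2 subjects are analysed, the objective is descriptive without pass or fail criteria, and a t-test may be done. Section 5.2.4 collects treated vessels, number of lesions, stents, lesion type and complexity, and notes that these are usually recorded for non-study patients too.

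**The concern.** Phase 2 has no allocation step. A patient joins the device group when someone decides to invite him or her, and that person knows that the case will be done with the contrast-reducing workflow. With entry criteria this wide, the eligible pool can run from a simple single lesion to complex multivessel work, and part of that difficulty can be judged beforehand from the planned vessels and lesion type.

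If harder cases are invited less often, for whatever reason, Phase 2 contrast volume falls without any contribution from the device. Data on enrolled patients alone cannot show who was not approached, and no later analysis can restore a consecutive series. The matter therefore belongs in the enrolment rules and cannot be left to an SAP.

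What is at stake is the estimate itself. It is the main product of the pilot and is intended to inform the pivotal study and, eventually, a contrast-reduction claim (section 3.1). An inflated reduction would make the pivotal study too small.

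**Working it through.** **Stated figures.** The protocol gives 20 patients in Phase 1 and 25 in Phase 2: 20 + 25 = 45, which agrees with sections 4.3.4 and 5.1. It gives no SD, effect size, alpha or power, so no sample-size calculation can be reproduced.

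**The enrolment rules side by side.**
- Who may enter: 4.3.1.1 and 4.3.1.2.
- When a patient counts as enrolled: 4.3.3, at consent, before any study procedure.
- What a Phase 2 patient receives: 4.4, the same for all and known in advance.
- Who must be invited, and who was passed over: not stated in 4.3.1 to 4.3.4.

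**Possible size.** All inputs here are assumptions except the 25 per group.
- The hardest share *q* of eligible patients is not invited, judged by a prior impression that correlates *r* with contrast volume.
- Impression and volume are normal; volume is in SD units.
- The 25 retrospective patients are an unselected sample of the same eligible population.
- There is no device effect.

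With *c* the (1 − *q*) quantile of the standard normal and φ its density, shift = −*r* × φ(*c*) / (1 − *q*).

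| *q* | *r* | φ(*c*)/(1 − *q*) | Shift (SD) |
|---|---|---|---|
| 10% | 0.3 | 0.1755/0.9 = 0.195 | −0.058 |
| 20% | 0.5 | 0.2800/0.8 = 0.350 | −0.175 |
| 30% | 0.5 | 0.3477/0.7 = 0.497 | −0.248 |

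**Against sampling error.** The standard error of a 25 v 25 difference is √(2/25) = 0.28 SD, so each of these shifts is below one standard error.

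**If the optional t-test is run** (two-sided 5% assumed, 48 df), the noncentrality is shift × √(25/2): 0.21, 0.62 and 0.88 in absolute value. The chance of a falsely significant reduction is then 3.9%, 8.8% and 13.6%, against 2.5% with no selection. Allowing for the slightly smaller variance in a selected group gives 4.0%, 9.1% and 14.2%.

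**Effect on the pivotal study.** Required sample size varies as 1/(effect)². Take a true reduction of 0.5 SD as an illustration. Planning on 0.558, 0.675 or 0.748 SD gives (0.5/0.558)² = 0.80, (0.5/0.675)² = 0.55 or (0.5/0.748)² = 0.45 of the patients needed.

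**The case against.** The strongest reply is that the point rests on silence in a declared pilot. Much of that reply stands.

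- A reader might take the phrase about careful selection as permission to choose easy cases. The sentence does not support that, because it ties selection to the listed criteria. Section 8 forbids enrolling patients who do not meet them, and sections 4.3.5 and 5.1 keep every enrolled Phase 2 patient in the analysis. What remains is that eligibility criteria say who can be invited, not who has to be.
- A reader might see the investigator-decision clause as a route for removing hard cases. It sits inside the kidney disease criterion and concerns renal status, not lesion difficulty. Nothing in the protocol shows that it lowers Phase 2 contrast volume.
- A reader might assume that the operator does the recruiting. Section 11 says only that the investigator or a designee obtains consent. The treatment is known in advance whoever invites the patient.
- A reader might infer that the bias must favour the device. The protocol does not say how the 25 retrospective patients are picked, so the net direction is open.
- The t-test is optional and there is no pass or fail rule, so false-positive rates are a secondary measure of harm.
- The items in section 5.2.4 offer a partial check, because they are also recorded for non-study patients. However, their stated use is to describe the Phase 2 subjects, and no comparison is planned.

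The open, non-randomised design is a deliberate choice for first insights and is not disputed here. That choice does not require the invitation of patients to be left open, and consecutive invitation fits within it.

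**Conclusion.** The point holds as a possibility that the enrolment rules leave open. It is not evidence that selection will take place. Phase 2 may consist of a non-representative, possibly simpler, subset of eligible patients, and the estimate passed to the pivotal study would carry that bias.

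The protocol does not give its size or net direction. The range of 0.06 to 0.25 SD depends wholly on the assumed skip rates of 10% to 30%, correlations of 0.3 to 0.5 and unselected retrospective patients. A different way of choosing those 25 could enlarge, offset or reverse it. Although smaller than the standard error, a shift of this kind is systematic and would not average out with more patients. The change is worth making because it is cheap before enrolment and cannot be made afterwards.

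**What to change.** In sections 4.3.1 and 4.3.3 add wording such as: *In Phase 2, every consecutive eligible patient scheduled for PCI on the study system is invited until 25 are enrolled. A screening log records each eligible patient not enrolled and the reason.*

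In addition:
- Leave the kidney exclusion as it is. Where it is applied by investigator decision, record that and the reason in the log before the procedure.
- Report the numbers eligible, invited and enrolled with the primary result.
- Tabulate the case-mix items of section 5.2.4 for both the Phase 2 and the retrospective patients.

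The cost is protocol wording, a short log kept by existing staff, and extraction of items that the protocol describes as typically recorded. There are no extra patients or procedures. Enrolment may be slightly slower, and the observed reduction may look less favourable if harder cases come in.
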